#### **11.1.4 Pregnancies**

The investigator must report to SARC any pregnancy occurring in a study subject, or in his partner, during the subject's participation in this study. The report should be submitted within the same timelines as an SAE, although a pregnancy per se is not considered an SAE.

For a study subject, the outcome of the pregnancy should be followed up carefully, and any abnormal outcome of the mother or the child should be reported.

For the pregnancy of a study subject's partner, all efforts should be made to obtain similar information on course and outcome, subject to the partner's consent.

#### **11.1.5 Further safety documentation**

Progressive disease

If progressive disease leads to signs and symptoms that meet the criteria for an SAE (i.e., hospitalization, disability, death, or important medical event), the signs and symptoms should be reported as an SAE and not the underlying progressive disease.

Death

If any subject dies during the trial or within 30 days of the end-of-treatment visit, the investigator will inform SARC and record the cause of death in detail (using the SAE Form) within 24 hours.

#### **11.1.6 Data Safety Monitoring**

##### **11.1.6.1 Data Safety Monitoring**

An Independent Data Monitoring Committee will be formed to monitor safety and efficacy. The IDMC will be comprised of two oncologists and a statistician experienced

in clinical trials.

#### **11.1.6.2 Additional Data Safety Monitoring**

The SARC Clinical Trials Review Committee convenes monthly and will provide safety oversight for this trial. The purpose of the Clinical Trials Review Committee is to review the status of the ongoing SARC studies, which includes but is not limited to:

- Review of all safety data (Serious Adverse Events reported)
- Review of any protocol violations
- Review of study progress/accrual
- Discussion of statistical aspects of protocol as appropriate.

The committee is chaired by the SARC Medical Officer, who is responsible for leading the meeting and providing medical oversight. Attendance includes all Principal Investigators on active SARC studies, SARC Research Project Managers, SARC President and a biostatistician.

Safety oversight for this trial is also supported by the SARC Clinical Research Committee, which is made of senior sarcoma investigators. This committee reviews the findings of the Clinical Research Committee on a monthly basis. This committee provides an additional level of medical oversight for this trial.

#### **11.1.7 Patient Accrual and Participating Centers**

There will be approximately 18 SARC centers collaborating to accrue patients to this study. We anticipate accrual will take approximately 18-24 months.

This trial will be posted at the [www.clinicaltrials.gov](http://www.clinicaltrials.gov) website.

### **11.2 Multi-Institutional Guidelines**

The trial coordinating center (Operations Center) will be SARC. Patients will be registered electronically via the study website and adverse events (as defined in section 7.0) will be reported to the SARC Operations Center.

#### *IRB approvals:*

The protocol must be approved by the treating institution prior to enrolling patients. Documentation of individual IRB approval for the current protocol must be provided to the SARC Operations Center prior to enrolling patients on the trial. In addition, documentation of approval of all protocol amendments and of yearly continuing review must be provide to the Research Project Manager either electronically or via mail to the following address:

SARC  
[name]  
Ann Arbor, MI 48105  
[contact]  
Email: [[contact]](mailto:[contact])

### *Patient Registration*

Patient registration will be centrally managed electronically via the study website (see section 4.2).

### *Data Collection and Toxicity Reporting*

Registration reports will be generated by the Operations Center to monitor patient accruals and completeness of registration data. Routine data quality reports will be generated to assess missing data and inconsistencies by the SARC. Any potential problems will be brought to the attention of the study Principal Investigator(s) for discussion and action.

Access to the password protected study website will be limited to individuals involved in the clinical trial including: SARC staff, overall Study and Cohort PIs, participating site PIs, research nurse and data managers responsible for this trial.

Shipment and receipt of specimens and imaging studies sent for correlative studies will be entered and tracked on the study website. Details regarding handling and shipping will be outlined in the study operations manual.

## **11.3 Data and Participating Institution Monitoring**

Data monitoring for this trial will be managed remotely. A data monitoring and site monitoring plan will be developed for this trial. Should areas of concern be identified through the remote monitoring process, an on-site monitoring visit may be warranted. Findings will be discussed with the overall study PI and Cohort PIs, participating site PIs, Clinical Trials Review Committee and the SARC medical officer.

## **11.4 Human Subjects Protection**

### **11.4.1 Rationale for Subject Selection**

Subjects of both genders and from all racial and ethnic groups are eligible for this trial if they meet the eligibility criteria as outlined in section 3.1. No groups will be excluded from participation in the trial.

### **11.4.2 Evaluation of the Benefits and Risks/Discomforts**

The primary risk to patients participating in this research study is from toxicity associated with regorafenib, which has been approved by the FDA for the treatment of metastatic

renal cancer and gastrointestinal stromal tumors. The primary objectives of this phase 2 study are for Cohorts A & B to compare PFS of subjects treated with regorafenib or placebo and for Cohort C to estimate PFS at 8 and 16 weeks. A crossover option will be available for patients who progress on placebo as outlined in Section 5.

### **11.4.3 Management of Patient Data**

All patient data will be captured and maintained in a study specific database with password-protected access. Data is entered using an assigned study subject identification number.

The data provided to those reviewing the results, for example the study statistician will include the subject identification numbers but will not include patient identifiable data.

The research samples obtained on this study will only be sent using the study subject identification number, which can only be linked to the patient at a given institution by the treating physician.

All documentation that contains personal health information that may include patient identifiable information will be maintained at the site to preserve patient confidentiality.

## **11.5 Premature termination of study**

This study may be closed prematurely for any of the following reasons:

- If risk-benefit ratio becomes unacceptable owing to, for example:
  - Safety findings from this study (e.g. SAEs)
  - Results of any interim analysis
  - Results of parallel clinical studies
  - Results of parallel animal studies  
(on e.g. toxicity, teratogenicity, carcinogenicity or reproduction toxicity).
- If the study conduct (e.g. recruitment rate; drop-out rate; data quality; protocol compliance) does not suggest a proper completion of the trial within a reasonable time frame.

The investigator has the right to close his/her center at any time.

For any of the above closures, the following applies:

- Closures should occur only after consultation between involved parties.
- All affected institutions (e.g. IEC(s)/IRB(s); competent authority(ies); study center; head of study center) must be informed as applicable according to local law.
- In case of a partial study closure, ongoing subjects, including those in post study follow-up, must be taken care of in an ethical manner.

Details for individual subject's withdrawal can be found in **Section 5.8**.

## **12. STATISTICAL CONSIDERATIONS**

### **12.1 Efficacy and safety variables**

#### **12.1.1 Efficacy variables**

Efficacy variables to analyze include:

- Progression free survival (PFS, as assessed by RECIST 1.1), defined as time from randomization (or 1st day of treatment, cohort C, D and E) to site determined radiographic tumor progression or death from any cause (whichever occurs first). For patients alive without progression, censoring occurs at the date of last tumor assessment. In PFS analyses, if the exact progression date is unknown, the date of progression is taken to be the date the first time at which progression can be declared
- Proportions of patients who are progression-free (and alive)
- Proportions of patients without progression or death at landmark times (in particular at 8 and 16 weeks)
- Overall survival is defined as the time from randomization (or 1st day of treatment, cohorts C, D and E) until death from any cause. Censoring occurs at the date of last contact.
- Disease-specific survival is defined as the time from randomization (or 1st day of treatment cohorts C, D and E) until death from sarcoma
- Time to progression (as assessed by RECIST 1.1), defined as time from randomization (or 1st day of treatment, cohort C) to centrally-determined radiographic tumor progression, censoring for death without progression. Progression is defined, according to RECIST 1.1, as a 20% increase from nadir and a minimum of 5 mm increase over the lowest sum, the appearance of one or more new target or non-target lesions, or unequivocal progression of existing non-target lesions determined by radiographic assessment. In TTP analyses, the exact progression date is unknown. Date of progression is taken to be the date the first time at which progression can be declared
- Change in target lesion size. Target lesion size will be measured by imaging methods. Tumor size will be measured as a unidimensional tumor measurement per RECIST 1.1.
- Overall response rate (ORR as assessed by RECIST 1.1) defined as the portion of patients evaluable for response who achieved partial response or better and stable disease or better

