## 5.6 Duration of Therapy

Treatment may continue until one of the following criteria applies:

- Disease progression as defined by RECIST 1.1
- Greater than 28 days have elapsed since the last dose of study drug
- Patient decides to withdraw from the study during the treatment phase of the study
- Patient decides to withdraw from the study during the follow up phase after completion of treatment on the study
- General or specific changes in the patient's condition render the patient unacceptable for further treatment in the judgment of the investigator.

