### 10.1.6 Progression-Free Survival (PFS), Time to progression (TTP)

PFS is defined as the duration of time from start of treatment to time of progression or death, whichever occurs first. TTP is defined as the duration of time from start of treatment to time of progression, omitting death.

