### 10.1.7 Response Review

A post hoc central radiology review will be conducted and data regarding PFS and TTP will be recalculated based on these measurements as an additional endpoint. However, the interpretation of the images from the individual site will be used for the primary endpoint of PFS. De-identified images will be stored in a SARC designated centrally located bank.

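### TTP is tied to central reads in 12.1.1 while PFS is site-read and 10.1.7 makes central review additional; no rule covers site progression without central progression

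*Combined protocol and SAP*

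**What the plan says.** Three sections of the combined protocol and SAP define the endpoint.

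- **12.1.1 Efficacy variables.** PFS runs from randomization (first day of treatment in cohorts C, D and E) "to site determined radiographic tumor progression or death from any cause". Its censoring rule is written out: "For patients alive without progression, censoring occurs at the date of last tumor assessment". TTP runs from randomization (first day of treatment, naming cohort C only) "to centrally-determined radiographic tumor progression, censoring for death without progression". Death is the only reason for censoring TTP that is given.
- **10.1.7 Response Review.** Central radiology review is post hoc, and "data regarding PFS and TTP will be recalculated based on these measurements as an additional endpoint". It adds that "the interpretation of the images from the individual site will be used for the primary endpoint of PFS".
- **10.1.6.** No reader is named and the clock differs: "TTP is defined as the duration of time from start of treatment to time of progression, omitting death".

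The conduct sections determine what happens after a site calls progression. Section 5.6 lists "Disease progression as defined by RECIST 1.1" as ending treatment, and 5.8 removes the patient from study on the same criteria. Section 5.7 then provides one phone call at 30 to 45 days, and the study calendar shows no imaging after the off-study visit. In cohorts A and B, 4.3 unblinds at progression so that placebo patients may cross over. None of these steps waits for a central read.

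TTP is a secondary endpoint in all cohorts (1.2). Section 12.5 analyses time-to-event secondary endpoints with Kaplan-Meier curves and a log-rank test. The exploratory growth modulation index (1.3) has TTP on regorafenib as its numerator.

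**The concern.** TTP is normally PFS with deaths censored, so the gap between the two shows how much of PFS is death without progression. As 12.1.1 is written, the gap also contains the difference between two readers. Because 10.1.7 speaks of recalculating TTP on central reads, it implies that a site-read TTP already exists. Two analysts could report different main TTP results and each cite the plan.

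The second issue is what the central read can observe. Scanning on assigned treatment continues only until the site calls progression. If central review does not agree at that scan, no later scan on assigned treatment exists in which central progression could appear. Censoring the patient there removes someone likely to be closer to progression than those who remain at risk. Counting scans after crossover instead mixes in open-label regorafenib. The plan chooses neither.

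**Working it through.** **1. The definitions side by side**

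| | PFS, 12.1.1 | TTP, 12.1.1 | 10.1.6 (both) | 10.1.7 (both) |
|---|---|---|---|---|
| Reader | site | central | not named | central, additional |
| Clock starts, A and B | randomization | randomization | start of treatment | not stated |
| Clock starts, C/D/E | first day of treatment, C, D, E | first day of treatment, C only | start of treatment | not stated |
| Censoring if alive without event | last tumor assessment | not stated | not stated | not stated |

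The start dates can differ materially. Patients are randomized at registration (4.3), and 9.1 allows up to 21 days from enrollment to day 1. That is 21/30.4375 = 0.69 months, against an assumed control median PFS of 2 months (12.2).

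**2. The plan's own figure**

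Section 12.2 asks for 42 PFS events at a hazard ratio of 0.4, one-sided 5% and 90% power. Schoenfeld's formula gives 4(1.645 + 1.282)²/(ln 0.4)² = 40.8, so 41 events. Power at 42 events is Φ(√42 × 0.916/2 − 1.645) = 0.907. The figure reproduces. It belongs to site-read PFS; no events or power are set for TTP.

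**3. Direction and size of the censoring effect**

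The documents give no site/central discordance rate, so this is an illustration. Assumptions: exponential times with medians of 2 and 5 months (the 12.2 PFS values); scans every 8 weeks to week 32, then every 12; no deaths. A fraction p of patients are called progressed by the site one scan before central review would call them, and scanning then stops. Central progression at the first scan cannot be called earlier.

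Let S₁ be the probability of no central progression at week 8, which is 8 × 7/30.4375 = 1.840 months.

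- Placebo: S₁ = 2^(−1.840/2) = 0.529. The 16-week value with continued scanning is S₁² = 0.279.
- Regorafenib: S₁ = 2^(−1.840/5) = 0.775. The 16-week value is S₁² = 0.600.

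At week 8, a fraction pS₁(1 − S₁) is censored, and all of these patients would have had the event at week 16. The Kaplan-Meier estimate at 16 weeks becomes S₁²/[1 − p(1 − S₁)].

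| p | Placebo | Regorafenib |
|---|---|---|
| 0 | 0.279 | 0.600 |
| 0.20 | 0.279/0.906 = 0.308 | 0.600/0.955 = 0.629 |
| 0.30 | 0.279/0.859 = 0.325 | 0.600/0.932 = 0.644 |

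The overstatement is about 3 to 5 percentage points in each arm. A simulation of 200,000 patients under the same assumptions gave 0.308 and 0.326 for placebo, and 0.627 and 0.643 for regorafenib.

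**4. Hazard ratio, from the same simulation**

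With continued scanning the central hazard ratio is about 0.48, not 0.40, because event times fall on the scan grid. At the first scan the ratio of event probabilities is (1 − 0.775)/(1 − 0.529) = 0.48. Only changes from 0.48 matter.

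| Early site calls, placebo/regorafenib | Observed central HR | Site-read HR |
|---|---|---|
| 20%/20% | 0.47 | 0.50 |
| 30%/30% | 0.46 | 0.50 |
| 30%/15% | 0.50 | 0.48 |
| 15%/30% | 0.43 | 0.51 |

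The bias in central TTP can go either way.

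**The case against.** A reader might infer that PFS and TTP cannot be compared at all. Section 10.1.7 does not support that: it plans central PFS beside central TTP, so a same-reader pair will exist. That restores comparability within the central reads. It does not settle which TTP is the main one, and central PFS has the same censoring problem.

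A reader might also infer that the plan orders censoring at site progression. It does not; the only rule given for TTP concerns death. For crossover patients, 1.2 assesses PFS and TTP on open-label drug, so later scans may exist, and 12.2 calls for intention-to-treat analysis. The gap is an unwritten rule, and informative censoring is one of its two possible consequences.

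The central reader may have been chosen for TTP deliberately, as the more objective one. Site reads are not free of error either: in step 4 the site-read hazard ratio also moves, and under early site calls site-read TTP is shorter than a complete central TTP would be. This objection has force. The case for site reads is that every site call supplies an event and that the reader matches PFS, not that sites read better.

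Finally, TTP is secondary, with no alpha or power assigned, and the simulated effects are modest. That stands, and it keeps the point minor.

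**Conclusion.** The point holds as a minor one. Sections 10.1.6, 10.1.7 and 12.1.1 do not agree on the reader or the start date for TTP, and no rule covers site progression without central progression. If 12.1.1 is followed, central TTP is either informatively censored or mixed with open-label drug. The end of scanning affects all cohorts; unblinding and crossover affect A and B only.

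The actual size is unknown. The 3 to 5 points at 16 weeks rest on the assumed 20-30% of early calls and on those patients being close to central progression. If the site calls were simply wrong, the censoring would be less informative.

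A reader might multiply a 20-30% disagreement rate by 42 and conclude that 8.4 to 12.6 events per randomized cohort become informative censorings. The documents do not support this. The rate is assumed, disagreement at a given scan includes earlier central calls (which remain TTP events), and the 42 PFS events may include deaths. Carrying such losses into a power figure would also mislead, since TTP has no power target.

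Primary site-read PFS, its 42 events and its one-sided 5% level are untouched.

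**What to change.** In 12.1.1, define TTP on site-determined progression, from the same start date as PFS (naming cohorts C, D and E), with the PFS rule for patients alive without progression. PFS and TTP then differ only by deaths without progression.

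Keep central-review PFS and TTP in 10.1.7 as the additional, sensitivity analyses. State that they censor at the last scan before crossover or the end of scanning, and that this censoring may be informative. Align 10.1.6 with 12.1.1 on reader and start date, and say which TTP feeds the growth modulation index.

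The cost is text in three sections; both sets of reads are already planned. The drawback is that the main secondary TTP loses the central read, which is still reported as sensitivity. Enrollment in cohorts A, B and C is complete, so the amendment should record its reason and be made before the central reads are analysed, so that the reader is not chosen after seeing results.

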## 1. OBJECTIVES

### 1.1 Primary Objective

**A. Cohort A (liposarcoma):** To compare the progression-free survival (PFS) of eligible subjects treated with regorafenib or placebo according to modified RECIST version 1.1.

**B. Cohort B (osteogenic sarcoma):** To compare the progression-free survival (PFS) of eligible subjects treated with regorafenib or placebo according to RECIST version 1.1.

**C. Cohort C (Ewing/Ewing-like sarcoma):** To estimate the RECIST 1.1 PFS rate of eligible subjects treated with regorafenib at 8 and 16 weeks.

**D. Cohort D (Rhabdomyosarcoma: Fusion-positive alveolar, Embryonal, Fusion-negative alveolar):** To estimate the RECIST 1.1 PFS rate of eligible subjects treated with regorafenib at 8 and 16 weeks. To estimate the RECIST 1.1 response rate (PR or better) of eligible patients treated with regorafenib at 8 weeks.

**E. Cohort E (mesenchymal chondrosarcoma):** To estimate the RECIST 1.1 PFS rate of eligible subjects treated with regorafenib at 24 weeks. To estimate the RECIST 1.1 response rate (PR or better) of eligible patients treated with regorafenib at 24 weeks.

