## **Week 8**

Off week from treatment.

Imaging studies for comparison to baseline to be conducted this week.

- The same modalities should be used throughout the study as baseline, unless allergies or other adverse events intervene).

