#### 10.1.1 Definitions

Evaluable for toxicity. All patients will be evaluable for toxicity from the time of their first treatment with regorafenib.

Evaluable for objective response. Only those patients who have measurable disease present at baseline, have received at least one cycle of therapy, and have had their disease re-evaluated will be considered evaluable for response. These patients will have their response classified according to the definitions stated below. (Note: Patients who exhibit objective disease progression prior to the end of cycle 1 will also be considered evaluable.)

Evaluable Non-Target Disease Response. Patients who have lesions present at baseline that are evaluable but do not meet the definitions of measurable disease, have received at least one cycle of therapy, and have had their disease re-evaluated will be considered evaluable for non-target disease. The response assessment is based on the presence, absence, or unequivocal progression of the lesions.

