## **12.2 Study Design/Endpoints**

### **Cohorts A and B (liposarcoma and osteosarcoma)**

Each of cohorts A and B will be studied using a randomized placebo controlled phase II design with a progression free survival endpoint. Outcomes will be determined on an intention to treat analysis.

Each cohort substudy will be powered to detect a difference of at least 3 months in median PFS, which has been discussed among expert sarcoma oncologists as a clinically meaningful difference in outcome. This corresponds to a median control group PFS of 2 months, median treatment group PFS of 5 months, and hazard ratio of 0.4 for treatment/control groups.

42 events are needed to detect a targeted difference with 90% power and 5% one-sided significance level. The final analysis of the primary PFS endpoint will be conducted when at least 42 patients had disease worsening. 48 eligible patients are expected to be randomized, to achieve the 42 expected events with an enrollment rate of 4 eligible patients per month per substudy. With the predicted accrual rate and PFS parameters, the 42 events are expected to occur in 16 months.

We will limit to a maximum of 16 patients per substudy A & B with WHO performance status of 2. There is no such limitation for substudy C.

Survival will be estimated by the Kaplan-Meier method. The treatment groups will be compared with a one-sided stratified log rank test. All analyses will be done in the intention-to-treat population.

We will conduct a prognostic factor analysis for PFS using a univariate Cox model; significant factors subsequently will be included in a multivariable Cox regression model (cutoff  $p < 0.05$ ). For a predictive analysis of PFS, Cox models will be generated with the investigated factor, treatment, and their interaction, with a significance value of  $p < 0.05$ . P-values will not be adjusted for multiple comparisons.

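### ORR is calculated on an evaluable subset that omits some treatment failures, contrary to the populations stated for Cohorts A/B and D/E, and its definition runs two rates together

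*Combined protocol and SAP*

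**What the plan says.** - **ORR definition (section 12.1.1):** "defined as the portion of patients evaluable for response who achieved partial response or better and stable disease or better".
- **Evaluable for response (section 10.1.1):** "Only those patients who have measurable disease present at baseline, have received at least one cycle of therapy, and have had their disease re-evaluated". A note adds one exception: "Patients who exhibit objective disease progression prior to the end of cycle 1 will also be considered evaluable".
- **First scheduled re-evaluation (section 9.2, Week 8):** "Imaging studies for comparison to baseline to be conducted this week".
- **Population for Cohorts A and B (section 12.2, under the heading for those cohorts):** "Outcomes will be determined on an intention to treat analysis", and later "All analyses will be done in the intention-to-treat population". Neither sentence makes an exception for response.
- **Cohort D objective (section 1.1):** "To estimate the RECIST 1.1 response rate (PR or better) of eligible patients treated with regorafenib at 8 weeks". Cohort E has the parallel sentence at 24 weeks. Section 1.2 lists ORR as a secondary objective in every cohort.
- **Disease control (section 12.2, Cohorts D and E):** CR, PR and stable disease together form a separately named rate. The decision rules are numbers of patients (at least 3 of 12 in D, at least 4 of 12 in E), and success is to be judged on the accrual actually reached.
- **Best overall response (Table 10.2):** there is an inevaluable category, but no text says whether such patients stay in the ORR denominator.

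**The concern.** A patient who dies, worsens clinically or stops for toxicity before a usable assessment has not responded. If such patients leave the denominator, the rate describes only those who lasted long enough to be assessed. These are aggressive diseases: the plan assumes a 2-month median PFS on control in A and B, and for Cohort C it cites a 1.3-month median with an active agent in Ewing sarcoma. Some early losses should be expected, and section 4.5 allows no replacement of dropouts.

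Three things are at stake. The reported ORR would be too high. Two analysts could follow different sections of the same plan and report different rates. In A and B, unequal loss between arms could distort the response comparison. Separately, a definition that names two thresholds does not tell the reader which one the ORR result will use.

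**Working it through.** **1. No stated figure to reproduce.** The documents give no expected ORR, no power for ORR and no expected non-evaluable share. What follows checks the definitions and shows a range.

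**2. Who stays in and who leaves under section 10.1.1.**

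| Patient | Evaluable? |
|---|---|
| Objective progression before the end of cycle 1 | Yes, by the note |
| At least one cycle, then stops and is scanned at the off-study visit (section 9.3) | Yes |
| At least one cycle, then dies or deteriorates with no repeat scan | No |
| Stops or dies in cycle 1 without objective progression, scanned or not | No |

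The last two rows are treatment failures. Under intention to treat (A/B), or among eligible treated patients (D/E), they belong in the denominator.

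**3. Effect on the rate.** Let x be responders, n all patients and k non-evaluable patients, with m = k/n, and let the k patients be non-responders. Then

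[x/(n−k)] ÷ [x/n] = n/(n−k) = 1/(1−m).

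| Assumed m | Factor | An all-patient rate of 10% is reported as |
|---|---|---|
| 5% | 1.05 | 10.5% |
| 10% | 1.11 | 11.1% |
| 20% | 1.25 | 12.5% |
| 30% | 1.43 | 14.3% |

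The factor is never below 1. With no responders the rate stays at zero. In one arm of A or B (48 randomized 1:1, so 24), 3 responders give 3/24 = 12.5%, but 3/20 = 15.0% if 4 are non-evaluable.

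**4. An illustration from the protocol's own background.** Section 2.4.3 reports a pediatric phase I study with 41 treated, 39 valid for efficacy, no CR, 1 PR and 15 with stable disease. The denominator factor is 41/39 = 1.05. That is another study with its own validity rule, so it is an example and not an estimate of m here.

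**5. Effect on a comparison in A or B.** Take equal results, 3/24 = 12.5% in each arm, and assume 5 non-evaluable in one arm and 1 in the other. The rates become 3/19 = 15.8% and 3/23 = 13.0%. The arm that loses more patients looks better, whichever arm that is.

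**6. Numerator.** On the counts in step 4, PR or better is 1/41 = 2.4% and stable disease or better is 16/41 = 39.0%. The two thresholds joined in section 12.1.1 can therefore give very different results. Read strictly, a patient must meet both, and the definition reduces to PR or better.

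**7. Decision rule in Cohort D.** Three controlled patients are 3/12 = 25.0%, or 3/10 = 30.0% if 2 are non-evaluable (assumed). The rule asks for 3 patients, so both pass. If the cutoff were re-derived for a smaller n at the 10% inactive rate, P(X ≥ 3) is 0.111 at n = 12, 0.070 at n = 10 and 0.053 at n = 9. A cutoff of 2 gives more than 0.22 at n = 9 or 10, so the cutoff would stay at 3.

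**The case against.** **The loss is narrow.** Section 9.3 asks for imaging at the off-study visit if it has not been done. Sections 5.1 and 10.1 provide for earlier scans on deterioration or symptoms. Section 7.1.1.6 expects progression on clinical grounds alone to be rare, and early objective progression is retained. This stands, and it argues for the lower part of the assumed range. It does not remove the problem: an off-study scan cannot rescue a patient who stopped in cycle 1 without progression, because the one-cycle condition still fails.

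**The intention-to-treat sentences do not govern the whole trial.** A reader might infer that they cover all cohorts. They stand under the Cohorts A and B heading, so the contradiction is direct only there. For D and E the conflict is with the population in section 1.1. For Cohort C no intention-to-treat sentence applies to ORR, and the case for a full denominator rests on bias alone.

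**The joined numerator is only loose drafting.** Largely true. A reader might infer that it inflates ORR, but the strict reading is PR or better, section 1.1 says the same for D and E, and section 12.2 names disease control separately. What remains is ambiguity about which rate is reported as ORR.

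**ORR in A and B is secondary.** Section 12.5 plans descriptive statistics for secondary endpoints, and the primary PFS test does not use the evaluable set. This limits the consequences but does not settle which population the ORR uses.

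**Conclusion.** The point holds in this form. Following sections 12.1.1 and 10.1.1 as written removes some treatment failures from the ORR denominator. It contradicts section 12.2 for Cohorts A and B and section 1.1 for the response objective in D and E. The direction is clear and the size is not: the factor is 1.05 to 1.43 for an assumed non-evaluable share of 5% to 30%. This rests on the excluded patients being non-responders. A patient who responded on less than one cycle would be an exception, and section 10.1.4.3 makes that unlikely because best response also depends on confirmation.

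Three stronger conclusions are not supported:

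- **That the evaluable set could turn a failed Cohort D or E into a success.** The rules count patients and refer to actual accrual, and no text ties disease control to the evaluable set.
- **That the A/B comparison is biased toward regorafenib.** Early toxicity stops on the active arm are plausible, but early deaths or deterioration on placebo would act the other way, and the documents give no rates for either.
- **That response is settled as a primary endpoint in D and E.** Section 1.1 lists it among the primary objectives, while the Synopsis lists only PFS rates.

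This should be corrected, but it does not threaten the primary analyses.

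**What to change.** Amend sections 10.1.1 and 12.1.1 as follows:

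1. Define two separately named rates: ORR (CR + PR) and disease control rate (CR + PR + SD).
2. Use all randomized patients as the denominator in Cohorts A and B, and all eligible treated patients in Cohorts C, D and E.
3. Count a patient with no post-baseline assessment as a non-responder and as not disease-controlled.
4. Retain the evaluable-only rate as a labelled sensitivity analysis, and report the number of non-evaluable patients and the reasons, by arm in A and B.

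The cost is protocol and SAP wording, with no added visits, scans or patients. Reported rates may be slightly lower. Section 3.1 records that enrollment in Cohorts A, B and C was complete as of amendment 5, so for those cohorts the change should be documented as made after accrual.
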